19.3. ANTIBODIES TO TEDUGLUTIDE

The number and percent of subjects with an antibody finding (Antibodies to Teduglutide Negative/Positive, Neutralizing Antibodies Present/ No Neutralizing Antibodies Present) will be summarized at baseline, EOT and EOS. Non-specific antibodies will be categorized as Negative.

Document:	\\quintiles.net\Enterprise\Apps\sasdata\SASa\sas\Shire\Teduglutide\Biostatistics\Documentation\SAP\TE D-C14-006_SAP_Final_V1.0_20170714		
Author:	PPD	Version Number:	Final V1.0
		Version Date:	14Jul2017
Template No:	CS_TP_BS016 – Revision 3	Reference:	CS_WI_BS005
Effective Date:	01May2012		

The follow-up antibody assessments after study completion will not be transferred from the lab vendor for any statistical analysis.

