6 STUDY EVALUATIONS AND PROCEDURES

6.1 Evaluations for Safety and Tolerability

Safety variables will be assessed by the following evaluations, according to Schedules of Evaluations and Procedures as outlined in [Table 6-1](#) and [Table 6-2](#). Safety variables for the standard of care group are displayed in [Table 6-3](#) and [Table 6-4](#).

- Adverse events, including GI symptoms. A GI Symptom History Worksheet will be completed daily during the screening period, prior to baseline. GI symptoms will be

recorded as none, mild, moderate, or severe. The principal investigator will assess the aggregate diary entries to determine a baseline of GI symptoms for each subject.

- Physical examinations
- Vital signs, including temperature, heart rate, and blood pressure, body weight, head circumference (up to 36 months of age), height or length, and trends on growth charts
- Electrocardiograms
- Laboratory safety data, including clinical chemistries, hematology, and urinalysis
- Change in urine output (collected or calculated volume)
- Fecal output (by volume or number of bowel movements per day)
- Antibodies to teduglutide (active treatment groups only). Samples for antibody analysis will be drawn at baseline and at the EOT (Week 24 or early termination) visits prior to the administration of teduglutide and at least 14 hours after the previous dose. One additional sample will be collected at the final visit 4 weeks after the EOT (EOS, Week 28). If subjects are determined to have positive/specific antibodies at Week 28 or EOS, they will be asked to return for a follow-up clinic visit 3 months post EOT for another antibody sample. If the subjects continued to have positive/specific antibodies at 3 months post EOT, they will be asked to return for a follow-up visit 6 months post-treatment in order to determine their antibody status.
- GI-specific testing (active treatment groups only) including colonoscopy or sigmoidoscopy, abdominal ultrasound, fecal occult blood testing, UGI/SBFT

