8.2 Safety and Tolerability Variables

The safety and tolerability variables include:

- Adverse events, including GI symptoms
- Physical examination
- Vital signs, including temperature, heart rate, blood pressure, body weight, head circumference (up to 36 months of age), height or length, and trends on growth charts
- Electrocardiograms
- Laboratory safety data, including clinical chemistries, hematology and urinalysis
- Change in urine output (collected or calculated volume)
- Fecal output (by volume or number of bowel movements per day)
- Antibodies to teduglutide (active treatment group only)
- GI-specific testing (active treatment groups only) including colonoscopy or sigmoidoscopy, abdominal ultrasound, fecal occult blood testing, UGI/SBFT

Adverse events will be coded using the current version of MedDRA. Treatment emergent AEs will be summarized by system organ class and preferred term for each treatment group. The number and percentage of subjects with AEs, SAEs, AEs that lead to discontinuation, study drug-related AEs (determined by the investigator), and AEs that lead to death will be summarized by treatment group. AEs will also be summarized by treatment group with regard to intensity and relationship to study drug. For AEs of special interest, the CTCAE grading system will be used as described in Section 6.1.4.

For laboratory tests, vital signs, body weight, ECG, and fluid balance variables, descriptive statistics (mean, median, standard deviation, minimum and maximum values, the number and percentage of subjects in specified categories) will be calculated to summarize the absolute values and change from baseline at each scheduled visit for each treatment group.

The number and percentage of subjects classified as having positive specific antibodies to teduglutide will be used to summarize the presence of antibodies for each treatment group.

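### The visit-by-visit antibody counts in SAP 19.3 do not generally show how many baseline-negative children became positive on each dose

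*SAP*

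**What the plan says.** SAP 19.3 is the whole of the planned antibody analysis. The categories are "Antibodies to Teduglutide Negative/Positive, Neutralizing Antibodies Present/ No Neutralizing Antibodies Present", and these "will be summarized at baseline, EOT and EOS". It adds that "Non-specific antibodies will be categorized as Negative". The samples taken later from children still positive at Week 28 do not enter: "The follow-up antibody assessments after study completion will not be transferred from the lab vendor for any statistical analysis". The section defines no treatment-emergent category, no shift from baseline, no count of subjects positive at any visit after dosing, and no denominator restricted to baseline-negative subjects.

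Protocol 8.2 plans its own summary by dose group: "The number and percentage of subjects classified as having positive specific antibodies to teduglutide will be used to summarize the presence of antibodies". Protocol 6.1 supplies the data: "Samples for antibody analysis will be drawn at baseline and at the EOT (Week 24 or early termination) visits", and one more sample follows at EOS (Week 28). Treated children therefore have three scheduled samples, one before the first dose and two after it.

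The SAP takes baseline into account for other safety data. Section 19.1 counts as treatment-emergent those adverse events that begin or worsen from the first dose onward. Section 19.2 plans shifts from baseline for quantitative haematology, chemistry and selected urinalysis results.

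**The concern.** The trial enrols children who have never had teduglutide (Protocol 4.1), and previous use of teduglutide or GLP-2 is an exclusion (Protocol 4.3, criterion 12). The natural immunogenicity question is how many of them become antibody-positive on each dose. That is a count of individual children followed from baseline to EOT and EOS. Three separate visit totals do not contain it. A child positive at both EOT and EOS appears in two rows, two different children positive at one visit each also appear in two rows, and the table cannot tell these cases apart. A child positive at baseline may or may not be among the later positives.

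At stake is a safety summary that would have to be given as a range, or rebuilt by hand with a definition and denominator chosen after the results are known.

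**Working it through.** Neither document gives an expected antibody rate or any antibody figure, so there is nothing to reproduce. The check is whether the planned table fixes the number wanted.

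**Inputs**
- n = 10 children per dose group, the minimum in Protocol 4.1.
- b, e and s are the numbers positive at baseline, EOT and EOS. All values below are assumptions for illustration.
- All three samples are taken as present in every child.

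**Quantity wanted.** The number negative at baseline and positive at EOT or EOS, out of n − b.

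**Limits set by the visit totals**
- Lower limit = max(0, max(e, s) − b). Every baseline-positive child stays positive, and the remaining EOT and EOS positives overlap as far as possible.
- Upper limit = min(n − b, e + s). No baseline-positive child is positive later, and EOT and EOS positives are different children as far as numbers allow.

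**Worked case: b = 1, e = 2, s = 3, so 9 children are baseline-negative.** The result depends on where the baseline-positive child falls later:

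| Baseline-positive child is later positive at | New positives at EOT | New positives at EOS | Newly positive at either |
|---|---|---|---|
| both visits | 1 | 2 | 2 to 3 |
| EOT only | 1 | 3 | 3 to 4 |
| EOS only | 2 | 2 | 2 to 4 |
| neither | 2 | 3 | 3 to 5 |

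Overall the range is 2 to 5 of 9: 2/9 = 22% and 5/9 = 56%. The formulas agree: max(2, 3) − 1 = 2 and min(9, 2 + 3) = 5.

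**Other assumed totals, n = 10 (full enumeration of the joint patterns)**

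| Positive at baseline / EOT / EOS | Newly positive at EOT | Newly positive at EOT or EOS |
|---|---|---|
| 0 / 3 / 3 | 3 | 3 to 6 |
| 1 / 3 / 3 | 2 to 3 | 2 to 6 |
| 2 / 3 / 3 | 1 to 3 | 1 to 6 |
| 2 / 2 / 2 | 0 to 2 | 0 to 4 |
| 0 / 3 / 0 | 3 | 3 |
| 0 / 0 / 3 | 0 | 3 |

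With no baseline positives the EOT row does give the number newly positive at EOT exactly. The number newly positive at either visit is still open in the 0 / 3 / 3 case, because the EOT and EOS overlap is unknown. It is fixed only in special cases, such as the last two rows. A count made child by child replaces each range with one number.

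**The case against.** Several stronger readings are tempting, and the documents do not support them.

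- **That SAP 19.3 departs from Protocol 8.2.** The protocol asks for the presence of specific antibodies by treatment group. A per-visit count of positive subjects, with non-specific results set to negative, is compatible with that. The SAP also states that it rests on protocol amendment 4, whereas the history in the supplied protocol runs only to amendment 2, so this text of 8.2 may not be the governing one.
- **That the table presents pre-existing antibodies as caused by the drug.** It does not. Baseline has its own row and nothing in the SAP attributes later positives to treatment. A reader can bound the number of new positives.
- **That no by-subject listing will exist.** SAP 19.3 names none, but the listing shells are in a separate file (SAP Appendix 4) that is not available here, and SAP 20 sends other collected data to appendix listings. Absence cannot be shown.

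It is also fair to say that baseline positives may be few or none in children without previous exposure. The upper limits are extreme as well: 5 of 9 requires the two EOT positives to be negative four weeks later, three different children to be positive at EOS, and the baseline-positive child to be negative at both visits. The study is descriptive with about 20 treated children, and no test depends on this row.

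All of that limits the weight of the point. It does not remove the gap: without baseline positives the EOT and EOS overlap is still untabulated, and a listing would let someone rebuild the count without settling its definition or denominator in advance.

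**Conclusion.** The point holds as a modest improvement to the planned summary. The visit-wise counts in SAP 19.3 do not generally determine how many baseline-negative children became antibody-positive on each dose, whether or not any child is positive at baseline. In the worked case the table leaves 2 to 5 of 9 open. That range depends on assumed visit counts and complete sampling; it gives the limits of what the table allows and does not estimate a likely error. The gap is in the specified summary only: the samples that answer the question are already scheduled.

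**What to change.** In SAP 19.3, keep the summary at baseline, EOT and EOS, and add:

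- By dose group and in total, the number and percent with treatment-emergent specific antibodies, defined as negative at baseline and positive at EOT or EOS. The denominator is baseline-negative subjects with at least one post-dose antibody sample. It needs to be written down because the SAP Appendix 1 default is all subjects in the group unless stated otherwise or the number at the time point is shown.
- The same row for neutralising antibodies.
- Any baseline-positive subjects, reported separately.
- Confirmation that the listing shells include a by-subject listing of antibody results.

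The cost is one extra table row, its neutralising counterpart, and a check of the shells. No new sample, visit or assay is needed.

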at 3 months post EOT, they will be asked to return for follow-up visit(s) up to 6 months post-treatment in order to determine their antibody status.

Safety and tolerability results will be evaluated by a Data Safety Monitoring Board (DSMB) approximately every 3 months during the active study period (date of the first subject's first dose to date of the last subject's last dose). The DSMB review will include all cumulative safety data (ie, adverse events, laboratory assessments, physical examinations, etc.) from study assessments through each cutoff period.

A schematic representation of the study design is displayed in [Figure 3-1](#).

Figure 3-1 Study Diagram

Note: The Standard of Care group follows the same visit schedule as the active treatment groups.

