Concomitant medication	X	X	X	X	X	X	X	X	X	X	X	X	X	X

EN = enteral nutrition; EOS = end of study; EOT = end of treatment; ET = early termination; PN/IV = parenteral nutrition/intravenous fluid

^a If fecal/occult blood is positive without explanation, then a colonoscopy/sigmoidoscopy may be warranted

^b Citrulline should be collected 2 to 4 hours postprandially, whenever possible.

^c Intake Diaries will collect data on PN/IV support volume, EN (formula and specialized electrolyte solutions), and regular diet/drink taken DAILY.

^d Urine/Stool Output Diary will collect data on urine and stool output for the 48 hours prior to the next scheduled visit or telephone contact.

^e Nutritional support includes PN/IV, EN feeds (formula and other specialized electrolyte solutions), and regular diet/drink.

^f Nutritional support adjustments can be made after review of the subject's intake and output data recorded on the diaries and the subject's safety lab data following the guidance for nutrition support adjustment provided in [Appendix 1](#).

^g Female subjects of child-bearing potential

^h Head circumference is to be collected as appropriate (ie, up to 36 months of age).

ⁱ At site visits, safety lab assessments consist of serum chemistry, hematology and urinalysis. For safety lab assessment done approximately 7 days following any PN/IV adjustment and/or in between site visits, safety labs consist of serum chemistry and urinalysis. Safety labs performed during site visits must be processed via central lab. Safety labs performed at alternate times in between site visits may be collected by a Home Health Agency and processed for submission to the central lab.

^j Antibody blood draw is to be taken prior to the last dose of study drug, at least 14 hours following the previous dose of study drug. Subjects who test positive/specific for antibodies to teduglutide at the Week 28 visit will have follow-up blood draws for positive/specific antibodies to teduglutide at approximately 3 months following the last dose of study drug. If antibodies are still positive/specific they will be collected again approximately 6 months after the last dose of study drug.

^k If a subject terminates from the study prematurely, all EOT procedures should be done at the time of termination and a follow-up visit should be scheduled 4 weeks later.

^l A visit to the site may be undertaken, if necessary, instead of a phone contact and completed as an Unscheduled Visit.

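### SAP 19.3 excludes every antibody sample taken after Week 28, so no planned output shows whether antibodies cleared or persisted

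*SAP*

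**What the plan says.** **Protocol.** Section 6.1 lists antibodies to teduglutide among the safety evaluations for the active groups, with samples at baseline, EOT and EOS. In the same bullet it adds a conditional follow-up. Children who are positive/specific at Week 28 or EOS are recalled: "they will be asked to return for a follow-up clinic visit 3 months post EOT for another antibody sample". If still positive, "they will be asked to return for a follow-up visit 6 months post-treatment in order to determine their antibody status". Section 3.1 says the same in slightly different words ("they will be asked to return for follow-up visit(s) up to 6 months post-treatment in order to determine their antibody status"), and footnote j to Table 6-2 repeats it: "If antibodies are still positive/specific they will be collected again approximately 6 months after the last dose of study drug". Section 8.2 makes antibodies a safety variable and plans a count and percentage: "subjects classified as having positive specific antibodies to teduglutide will be used to summarize the presence of antibodies for each treatment group". It names no time point. Section 7.1 says that data not entered on the eCRF, with laboratory results as the example, go from the vendor to the sponsor for inclusion in the database.

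**SAP.** Section 19.3 says that antibody findings, both positive/negative and neutralising/not neutralising, "will be summarized at baseline, EOT and EOS". It then sets the rule for later samples: "The follow-up antibody assessments after study completion will not be transferred from the lab vendor for any statistical analysis". Section 8.3 includes all available data in the safety analysis. Section 4.3 declares no change of analysis from the protocol. No reason is given for the exclusion.

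**Versions.** The SAP is written against protocol Amendment 4 (15 March 2016). The protocol supplied runs to Amendment 2 (06 October 2015). The rule in SAP 19.3 itself shows that follow-up antibody assessments still exist under the later version.

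**The concern.** The recall visits have one stated purpose, to find out a child's antibody status after treatment has stopped. They cost extra visits and blood draws in a paediatric population. The SAP summarises antibodies only up to four weeks after treatment and rules the later samples out of analysis.

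At stake is one descriptive safety result: among children who were antibody positive at EOS, how many cleared and how many stayed positive. With about 20 treated children planned, each positive child is a noticeable part of the safety record. That the study is purely descriptive is no obstacle, because a listing and a count need no inference.

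**Working it through.** The documents give no figure to reproduce. The check is one of timing and of comparing texts.

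**1. Do all recall samples fall under the exclusion?**
- Protocol Table 6-2 puts EOT at Day 168 and EOS at Day 196, so EOS is 196 − 168 = 28 days after EOT.
- SAP section 10 treats completion as running through Week 28 or EOS.
- Assumption: 3 and 6 months are about 91 and 182 days.
- 3-month sample: 168 + 91 = Day 259, which is 259 − 196 = 63 days after EOS.
- 6-month sample: 168 + 182 = Day 350, which is 350 − 196 = 154 days after EOS.
- A child who stops early has EOS four weeks after that child's own EOT, so the gaps (91 − 28 = 63 and 182 − 28 = 154 days) are the same. The ±4-day window at EOS does not change this.

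Every recall sample is therefore taken after study completion, and the exclusion covers all of them.

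**2. Does another part of the SAP bring them back?**
- Section 20 sends to listings other collected data that the SAP has not already described. Follow-up antibody results are described in 19.3, and excluded there.
- Section 19.2.1 gives local laboratory results a listing even though they are kept out of the summaries. Follow-up antibodies get no such listing.
- Sections 8.3 and 19.3 are not reconciled.

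**3. Which post-treatment antibody questions do the planned outputs answer?**

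| Question | Planned output |
|---|---|
| Positive or neutralising at EOT | Yes, SAP 19.3 |
| Positive or neutralising four weeks after EOT | Yes, SAP 19.3 |
| Still positive or cleared 3 months after EOT | None |
| Still positive or cleared 6 months after EOT, if positive at 3 months | None |

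**4. How many children?** Let *k* be the number positive/specific at EOS. The documents give no positivity rate, so *k* could be anything from 0 to the roughly 20 children planned for treatment. If *k* is 0, the rule has no effect. Otherwise, the results of all children who return are left out. The 6-month group is at most as large as the 3-month group, because only children still positive at 3 months are asked back.

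**The case against.** The strongest reply is that this is an open cut-off and not an oversight. The protocol calls Week 28 the one final scheduled clinic visit, and the recalls are conditional follow-up of individuals beyond it. Section 8.2 sets no time point, so the SAP's summaries at the three scheduled draws can be said to satisfy it. Results may also arrive after database lock. And the recall wording quoted here comes from Amendment 2, so the schedule and purpose under Amendment 4 cannot be checked.

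Much of this stands, and it rules out several stronger readings that a reader might infer:

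- *That the results will never leave the laboratory or be seen by anyone.* The SAP bars transfer for statistical analysis. It does not bar individual review, a narrative or a separate laboratory report, although neither document plans one.
- *That the SAP drops a table the protocol promised.* No protocol section specifies a table of 3- or 6-month results. For the same reason, the statement in SAP 4.3 that nothing has changed is not shown to be false.
- *That only the EOS result will be reported.* Baseline and EOT are summarised too, with neutralising status.

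The reply does not remove the gap. The protocol places the recalls inside the antibody safety evaluation and states their purpose. Late arrival is a reason for an addendum, and the SAP does not offer it as a reason for exclusion. The version difference is a caveat on the detail, because the SAP's own sentence confirms that follow-up assessments are made.

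**Conclusion.** The point holds as a gap between collection and planned reporting. All samples taken after EOS are outside the analysis, and no planned output shows clearance or persistence of antibodies after Week 28. The tension with protocol 7.1 and SAP 8.3 is real, though short of a flat contradiction: one concerns the database and the other concerns whatever data are available.

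The consequence is limited. The primary endpoint, the other efficacy results and the antibody summaries through EOS are unaffected. The number of children is unknown and may be zero; no estimate can be drawn from the documents.

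The conclusion assumes that 3 and 6 months are roughly 91 and 182 days after EOT, and that the recall scheme under Amendment 4 is broadly that of Amendment 2. This is a worthwhile and inexpensive improvement, not a defect in the main analysis.

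**What to change.** Replace the exclusion sentence in SAP 19.3 with a rule along these lines: the 3- and 6-month antibody results will be transferred and listed by subject; among subjects positive at EOS, the numbers still positive, neutralising (where tested), cleared and not sampled will be given by dose group at each recall time.

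Two details should be settled in the wording. A child who is negative at 3 months is not due at 6 months and should be counted as cleared, not as missing. A child who was asked back but did not come should be counted as not sampled, so that the denominator remains all children positive at EOS.

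If results arrive after database lock, issue them as an addendum to the study report; the main lock need not wait. Check the recall schedule against Amendment 4 before finalising the text.

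The cost is one late data transfer, one listing and one count. No planned analysis changes.

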19.4. GASTROINTESTINAL-SPECIFIC TESTING

GI-specific testing will be reported for the teduglutide treatment arm only. The clinically significant abnormal results will be presented in a data listing. The results of upper gastrointestinal (GI) series with small bowel follow through, abdominal ultrasound, and colonoscopy or sigmoidoscopy will be reported as 'Normal', 'Abnormal, not clinically significant', or 'Abnormal, clinically significant'. Fecal occult blood testing will be reported as 'Negative', 'Positive, not clinically significant', 'Positive, clinically significant'.

